Methemoglobin	X	X	X	X	X			X	Collect predose Cycle 1 Days 1, 8, 15, 22, each subsequent Cycle Day 1 and EOT. If elevated, draw reticulocyte count, LDH, and haptoglobin. Additional collections to be drawn as clinically indicated.
CBC with Differential and Platelets	X	X	X	X	X			X	Predose.
LFT Assessments	X	X	X	X	X			X	Predose; includes AST, ALT, total bilirubin, direct bilirubin (only if total bilirubin is elevated), alkaline phosphatase, and GGT (only when alkaline phosphatase is increased to ≥ Grade 2).
Thyroid Function Tests	X				X			X	If collected at screening, do not repeat on Cycle 1 Day 1. Collect

Table 5.1-15: On-treatment Procedural Table for QTc Substudy (BMS-986205 + Nivolumab)

Procedure	Cycle 1				Cycles 2+			End of Treatment ^{a,b,c}	Notes
	Day 1	Day 8	Day 15	Day 22	Day 1	Day 15 (±2 days)	Days 22 (+7 days) ^d		
									every 2 cycles, predose, beginning with Cycle 3 Day 1 and at the end of treatment. To include TSH with reflex testing (free T3 and free T4). Results should be examined by the investigator or appropriate designee within 48 hours of dose administration.
Pregnancy Test (WOCBP)	X				X			X	Serum or urine pregnancy test must be performed (urine pregnancy test: minimum sensitivity 25 IU/L or equivalent units of hCG) within 24 hours prior to administration of study drug. If pregnancy test is positive, hold all study drugs and perform confirmatory testing. If pregnancy is confirmed, permanently discontinue all study drug and immediately notify Sponsor per Section 6.5 .

Adverse Event Reporting and Concomitant Medication Assessments

Concomitant Medication Assessments	X	X	X	X	X	X	X	X	Review prior to dosing.
Monitor for Nonserious Adverse Events	X	X	X	X	X	X	X	X	Nonserious AEs will be collected starting with the first dose of study drug and through 100 days after completion of study drugs (or 30 days if subject only received BMS-

Table 5.1-15: On-treatment Procedural Table for QTc Substudy (BMS-986205 + Nivolumab)

Procedure	Cycle 1				Cycles 2+			End of Treatment ^{a,b,c}	Notes
	Day 1	Day 8	Day 15	Day 22	Day 1	Day 15 (±2 days)	Days 22 (+7 days) ^d		
									986205).
Monitor for Serious Adverse Events	X	X	X	X	X	X	X	X	All SAEs must be collected from the date of subject's written consent until 100 days after completion of study drugs (or 30 days if subject only received BMS-986205) or subject's participation in the study if the last scheduled visit occurs at a later time. eSAEs should be approved in the BMS EDC tool within 5 business days of entry.
Sample Collection									
Pharmacokinetic Assessments	See Section 5.5.4								
Immunogenicity Assessments	See Section 5.5.4								
Efficacy Assessments	See Section 5.4								

Table 5.1-15: On-treatment Procedural Table for QTc Substudy (BMS-986205 + Nivolumab)

Procedure	Cycle 1				Cycles 2+			End of Treatment ^{a,b,c}	Notes
	Day 1	Day 8	Day 15	Day 22	Day 1	Day 15 (±2 days)	Days 22 (+7 days) ^d		
Study Drug Administration									Details regarding preparation and administration are provided in the site training materials.
BMS-986205 Administration	X	Continuous daily dosing during all cycles							BMS-986205 administration must be performed daily. BMS-986205 must be administered with a light meal approximately the same time each day.
Nivolumab Administration	X				X				After the first nivolumab infusion, subjects should be monitored per local/institutional guidelines. If no such guidelines exist, an observation period of 2 hours after the end of the nivolumab infusion is suggested.
Pill Diary	X	Pill diary must be completed with each administered daily dose of BMS-986205						X	Review pill diary during each visit for compliance of daily administration of BMS-986205. Collect pill diary at the completion of each cycle and EOT.

^a EOT is defined as the visit where decision is made to discontinue the subject from treatment.

^b For subjects who complete all scheduled cycles of therapy, the EOT visit will be the same as the last scheduled and completed on-treatment visit (eg, Cycle 2 Day 22) and the start of the Week 1 Clinical/Safety Follow-up visit.

^c For subjects who do not complete all scheduled cycles of therapy, the EOT visit will be the most recent on-treatment visit (with all available safety and response data), does not need to be repeated, and will be considered the start of the Week 1 Clinical/Safety Follow-up visit.

^d Concomitant medication assessment and monitoring for nonserious AEs from Days 22 to 28 must be recorded on the next subject visit. For SAE, the guidance provided in [Section 6.1](#) must be followed.

Abbreviations: AE = adverse event; ALT = alanine aminotransferase; AST = aspartate aminotransferase; BMS EDC = Bristol-Myers Squibb Electronic Data Capture; BUN = blood urea nitrogen; CBC = complete blood count; CR = complete response; ECG = electrocardiogram; EOT = end of treatment; GGT = gamma-glutamyl transferase; hCG = human chorionic gonadotropin; IVRS = Interactive Voice Response System; IWG = International Working Group; LDH = lactate dehydrogenase; LFT = liver function test; PE = physical examination; Q2W = every 2 weeks; Q4W = every 4 weeks; RECIST = Response Evaluation Criteria In Solid Tumors; SAE = serious adverse event; TSH = thyroid-stimulating hormone; VS = vital signs; WOCBP = women of childbearing potential.

5.1.1 *Retesting During Screening or Lead-in Period*

Any new result will override the previous result (ie, the most current result prior to Randomization) and is the value by which study inclusion will be assessed, as it represents the subject's most current, clinical state.

Laboratory parameters and/or assessments that are included in [Table 5.1-1](#) may be repeated in an effort to find all possible well-qualified subjects. Consultation with the medical monitor may be needed to identify whether repeat testing of any particular parameter is clinically relevant.

Retesting is limited to these specific laboratory parameters and/or assessments.

5.2 *Study Materials*

The site will provide all required materials for the tests performed locally (ie, relevant clinical laboratory tests and urine drug screens). The site will have available a well-calibrated scale for recording body weight, a 12-lead ECG machine, and a calibrated sphygmomanometer and thermometer for vital signs assessments. A current and fully-stocked (advanced cardiac life support or basic cardiac life support) cart will be immediately available on the premises. The site will have urine collection containers, a refrigerated centrifuge, a monitored and alarmed refrigerator, and freezer (-20°C or below), as well as containers and dry ice for shipment and storage of blood and urine samples. The site will provide all materials required for accurate source documentation of study activities and for housing the subjects during the study. BMS will supply study medications.

BMS will provide a BMS-approved protocol and any amendments or administrative letters (if required) and IB. CRFs (electronic or hard copy) will be provided by BMS. BMS/The Central Laboratory will provide labels and tubes for the collection of blood samples for PK/biomarker analysis.

Additionally, the IVRS manual and pharmacy manual will also be provided.

5.3 *Safety Assessments*

AEs will be assessed continuously during the study and for 100 days after the last dose of study drug. AEs will be evaluated according to the NCI CTCAE v4.03 and should be followed per requirements in [Sections 6.1.1](#) and [6.2.1](#). AEs will be coded using the most current version of Medical Dictionary for Regulatory Activities (MedDRA) and reviewed for potential significance and importance. Subjects should be followed until all treatment-related AEs have recovered to baseline or are deemed irreversible by the investigator.

Protocol-specified assessments are detailed in [Section 5.1](#).

5.3.1 *Imaging Assessment for the Study*

Any incidental findings of potential clinical relevance that are not directly associated with the objectives of the protocol should be evaluated and handled by the study investigator as per standard medical/clinical judgment

5.3.2 *Laboratory Test Assessments*

A local laboratory will perform the analyses and will provide reference ranges for these tests. Results of clinical laboratory tests performed up to Day -1 must be available prior to dosing. The following clinical laboratory tests will be performed:

Hematology

Hemoglobin
Hematocrit
Total leukocyte count, including differential
Platelet count
Methemoglobin
Reticulocyte counts and haptoglobin (at baseline and reflex when methemoglobin is elevated)
Ferritin (at Screening)
Glucose 6-Phosphate Dehydrogenase deficiency testing (at screening)

Serum Chemistry

Aspartate aminotransferase	Total Protein
Alanine aminotransferase	Albumin
Total bilirubin	Sodium
Direct bilirubin	Potassium
Alkaline phosphatase	Chloride
Lactate dehydrogenase	Calcium
Creatinine	Phosphorus
Blood urea nitrogen	Magnesium
Uric acid	Creatinine clearance (CrCl)- screening only
Glucose (Fasting at screening only)	Bicarbonate/carbon dioxide
Amylase	
Lipase	
Gamma-glutamyl transferase only when alkaline phosphatase is \geq Grade 2	

Urinalysis (at screening)

Protein
Glucose
Blood
Leukocyte esterase
Specific gravity
pH
Other:
24 hour urine collection for testing of p-chloroaniline

Serology

Serum for hepatitis C antibody (if Hepatitis C antibody is positive reflex to hepatitis C RNA) or hepatitis C RNA, hepatitis B surface antigen, HPV status, HIV-1 and HIV-2 antibodies. (Testing for HIV-1 and HIV-2 must be performed at sites where mandated by local requirements)

Other Analyses

Pregnancy test (WOCBP only)

TSH with reflex to free T3 and free T4 as applicable.

FSH (if needed to document postmenopausal status as defined in [Section 3.3.3](#))

Results of all laboratory tests required by this protocol must be provided to BMS, either recorded on the laboratory pages of the CRF or by another mechanism as agreed upon between the investigator and BMS (eg, provided electronically). If the units of a test result differ from those printed on the CRF, the recorded laboratory values must specify the correct units. Any abnormal laboratory test result considered clinically significant by the investigator must be recorded on the appropriate AE page of the CRF (see [Section 6.3](#)).

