Re-treatment may be allowed in this study with disease progression during follow-up. Subjects completing approximately 48 weeks of study treatment or who discontinue therapy due to a CR, who enter Safety/Survival/Long-term Follow-up with ongoing disease control (CR, PR, or SD) for reasons other than drug-related toxicity, may be eligible for re-treatment upon subsequent confirmed disease progression within 12 months of the last dose of study drug, on a case-by-case basis, after careful evaluation and discussion with the BMS Medical Monitor to determine whether the benefit/risk ratio supports administration of further study drug. Subjects meeting criteria for re-treatment will be treated for a maximum duration of 2 years from first dose of nivolumab, with the originally assigned dose regimen (eg, same dose and dose schedule administered during the initial treatment period) or modified dose regimen, unless that dose and schedule were subsequently found to exceed the MTD, in which case the subject will be treated at the next lower or alternate dose and schedule (see [Table 4.5.3-1](#)). Subjects entering this phase will follow the same Time and Events schedule as outlined in [Section 5](#). Samples for PK will be collected less frequently. During re-treatment, pharmacodynamic biomarker samples obtained from blood will be collected as outlined in [Section 5.7](#).

The treatment and follow-up schematic for Parts 1, 2, and 3, and the pharmacology substudy is presented in [Figure 3.1.4-1](#). The study design schematic for the clinical pharmacology substudy is presented in [Figure 3.1.4-2](#).

[figure not shown]
Figure 3.1.4-1: Treatment and Follow-Up Schematic for CA017003--All Study Parts

Note: For Part 3 bladder cohort, Additional Treatment will not include ipilimumab

Abbreviations: CR = complete response; EOT= end of treatment; PD = progressive disease; PI = principal investigator; PR= partial response; SD = stable disease.

Figure 3.1.4-2: Study Schematic of Clinical Pharmacology QTc Substudy

*: Baseline ECGs should be collected prior to the start of Cycle 0 (Day -1 preferred, up to 5 days prior to Cycle 0 is allowed).

Abbreviations: ECG = electrocardiogram; Q4W = every 4 weeks; QD = once daily.

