Dose Modification Criteria for Drug-related Adverse Events	BMS-986205 Monotherapy Modification at the Next Dose (Part 1 Only)	BMS-986205 Combination Modification at the Next Dose (Parts 1, 2 and 3)
Methemoglobin ≥ 15%	Decrease 1 level of BMS-986205	Interrupt dosing until improvement and decrease 1 level of BMS-986205 in combination with same dose of nivolumab or nivolumab and ipilimumab.
Methemoglobinemia with Grade 3 AEs such as hypoxia and hemolysis	Interrupt BMS-986205. Continuation of BMS-986205 after recovery at a lower dose level may be considered after discussion with the Study Director/Medical Monitor. Subjects may proceed to get nivolumab monotherapy.	Interrupt BMS-986205. Continuation of BMS-986205 after recovery at a lower dose level may be considered after discussion with the Study Director/Medical Monitor. Subjects may proceed to get nivolumab monotherapy or nivolumab and ipilimumab.
Methemoglobinemia with Grade 4 AEs such as hypoxia and hemolysis	Permanent discontinuation of BMS-986205. Subjects may proceed to get nivolumab monotherapy.	Permanent discontinuation of BMS-986205. However, treatment with nivolumab or nivolumab and ipilimumab may continue after discussion between PI and Medical Monitor.
QTcF > 500 msec confirmed by at least 1 repeat ECG and at least 60 msec above baseline	Interrupt if needed to optimize electrolyte management. If persists after electrolyte optimization (including dose modification of BMS-986205, if necessary), discontinue. Subjects may proceed to get nivolumab monotherapy.	Interrupt if needed to optimize electrolyte management. If persists after electrolyte optimization (including dose modification of BMS-986205, if necessary), discontinue. However, treatment with nivolumab or nivolumab and ipilimumab may continue after discussion between PI and Medical Monitor.
Any other drug-related ≥ Grade 3 adverse event that does not meet permanent discontinuation criteria (Section 4.5.6)	Decrease 1 level of BMS-986205	Decrease 1 level of BMS-986205 in combination with same dose of nivolumab or nivolumab and ipilimumab.
Grade 2 LFT abnormalities that do not resolve within 1 week	Interrupt BMS-986205. Continuation of BMS-986205 after recovery at a lower dose level may be considered after discussion with the Study Director/Medical Monitor. Subjects may proceed to get nivolumab monotherapy.	NA
Grade 2 LFT abnormalities	Interrupt dosing until improvement to	NA

Table 4.5.3-1: Dose Modifications

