Safety Assessments									
Complete Physical Examination	X				X				
Symptom-directed PE			X			Q2W Nivo dosing only		X	

Table 5.1-3: On-treatment Procedural Outline (BMS-986205 + Nivolumab Part 1 Dose Escalation and Part 2 Dose Expansion)

Procedure	Cycle 1 (4 weeks)				Cycles 2+ (4 weeks)			End of Treatment ^{a,b,c}	Notes
	Day 1	Day 8	Day 15	Day 22	Day 1	Day 15 (±2 days)	Day 22 (+7 days) ^d		
Vital Signs and Oxygen Saturations	X	X	X	X	X	Q2W Nivo dosing only		X	Includes temperature, seated blood pressure, and heart rate. Blood pressure and heart rate should be measured after the subject has been seated quietly for at least 5 minutes. For nivolumab, VS should be obtained prior to the infusion and then every 30 minutes (± 10 minutes) until 1 hour following completion of the infusion, except on Cycle 1 Days 1 and 15 (for subjects receiving nivolumab 240 mg Q2W) and on Cycle 1 Day 1 (for subjects receiving nivolumab 480 mg Q4W) when VS will be obtained until 4 hours following completion of the infusion. If any vital sign is abnormal (based upon clinician assessment) at the final check, the subject must be observed further for a period of time, as clinically indicated.
12-lead ECG	X				X				12-lead ECGs should be recorded after the subject has been supine for at least 5 minutes. ECGs must be collected predose on Day 1 of each cycle.

Table 5.1-3: On-treatment Procedural Outline (BMS-986205 + Nivolumab Part 1 Dose Escalation and Part 2 Dose Expansion)

Procedure	Cycle 1 (4 weeks)				Cycles 2+ (4 weeks)			End of Treatment ^{a,b,c}	Notes
	Day 1	Day 8	Day 15	Day 22	Day 1	Day 15 (±2 days)	Day 22 (+7 days) ^d		
Laboratory Tests	
On-study laboratory tests (including pregnancy testing) to be done on site/local. Laboratory tests do not need to be repeated on Day 1 for Cycles 1 and onward, if completed within the last 72 hours.
 
All laboratory testing will be done weekly for Cycle 1 only, unless otherwise specified.
								
Chemistry (Excluding LFTs)	X	X	X	X	X	Q2W Nivo dosing only		X	Predose; includes assessments for sodium, potassium, chloride, total serum calcium, magnesium, bicarbonate/carbon dioxide, phosphorus, BUN, creatinine, glucose, total protein, albumin, amylase, lipase, and LDH.
Methemoglobin	X	X	X	X	X			X	
Collect predose.
 
Collected once per cycle from Cycle 2 on, or more frequently as clinical indicated.
 
If elevated, draw reticulocyte count, LDH, and haptoglobin.

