												until 1 hour following completion of the last infusion except on Cycle 1 Day 1 when VS will be obtained until 4 hours following completion of both infusions. If any vital sign is abnormal (based upon clinician assessment) at the final check, the subject must be observed further for a period of time, as clinically indicated.
12-lead ECG	X							X				12-lead ECGs should be recorded after the subject has been supine for at least 5 minutes. ECGs must be collected at predose on Day 1 of each cycle.

Table 5.1-4: On-treatment Procedural Outline--Part 3 (BMS-986205, Nivolumab, and Ipilimumab): Melanoma and Mixed Tumor Type

Procedure	Cycle 1 (8 weeks)							Cycles 2+ (8 weeks)			End of Treatment a,b,c	Notes
	Day 1	Day 8	Day 15	Day 22 (±2 days)	Day 29	Day 36 (±2 days)	Day 43 (±2 days)	Day 1	Day 15 (±2 days)	Day 29		
Laboratory Tests	On-study laboratory tests (including pregnancy testing) to be done on site/local. Laboratory tests do not need to be repeated on Day 1 if completed within the last 72 hours.											
Chemistry (Excluding LFTs)	X	X	X	X	X	X	X	X	C2 only	X	X	Predose; includes assessments for sodium, potassium, chloride, total serum calcium, magnesium, bicarbonate/carbon dioxide, phosphorus, BUN, creatinine, glucose, total protein, albumin, amylase, lipase, and LDH.
Methemoglobin	X	X	X	X	X	X	X	X	C2 only	X	X	Predose; additional assessments as clinically indicated. If elevated, draw reticulocyte count, LDH, and haptoglobin.
CBC with Differential and Platelets	X	X	X	X	X	X	X	X	C2 only	X	X	Predose.
LFT Assessments	X	X	X	X	X	X	X	X	C2 only	X	X	Predose; includes AST, ALT, total bilirubin, direct bilirubin (only if total bilirubin is elevated), alkaline phosphatase, and GGT (only when alkaline phosphatase is increased)

Table 5.1-4: On-treatment Procedural Outline--Part 3 (BMS-986205, Nivolumab, and Ipilimumab): Melanoma and Mixed Tumor Type

Procedure	Cycle 1 (8 weeks)							Cycles 2+ (8 weeks)			End of Treatment a,b,c	Notes
	Day 1	Day 8	Day 15	Day 22 (±2 days)	Day 29	Day 36 (±2 days)	Day 43 (±2 days)	Day 1	Day 15 (±2 days)	Day 29		
												to ≥ Grade 2).
Thyroid Function Tests	X				X			X		X	X	If collected at screening do not repeat on Cycle 1 Day 1. To include TSH with reflex testing to free T3 and free T4 if TSH abnormal. Results should be examined by the investigator or appropriate designee within 48 hours of dose administration.

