Procedure	Day 0 ^a	Notes
Safety Assessments		
Informed Consent	X	Subjects must re-consented.
Complete Physical Examination	X	If the screening PE is performed within 1 day of dosing on Cycle 1 Day 1, then a single examination may count as both the screening and predose evaluation.
ECOG Performance Status	X	ECOG Performance Status (Appendix 2).
Physical Measurements	X	Weight
Vital Signs	X	Includes body temperature, respiratory rate, seated blood pressure, and heart rate. Blood pressure, respiratory rate, and heart rate should be measured after the subject has been seated quietly for at least 5 minutes.
Oxygen Saturation	X	Pulse oximetry collected at rest.
Electrocardiogram	X	12-lead ECG should be recorded after the subject has been supine for at least 5 minutes if not done within the last 30 days.
Laboratory Tests		
Chemistry (Excluding LFTs)	X	Includes assessments for sodium, potassium, chloride, total serum calcium, magnesium, bicarbonate/carbon dioxide, phosphorus, BUN, creatinine, creatinine clearance, fasting glucose, total protein, albumin, amylase, lipase, uric acid, ferritin, and LDH.
Methemoglobin	X	Methemoglobin levels to be assessed on arterial or venous blood sample (performed locally).
CBC with Differential and Platelets	X	
LFT Assessments	X	Includes AST, ALT, total bilirubin, direct bilirubin (only if total bilirubin is elevated), alkaline phosphatase, and GGT (only when alkaline phosphatase is increased to \geq Grade 2).

Table 5.1-8: Re-treatment Day 0 Procedural Outline (CA017003)

Procedure	Day 0 ^a	Notes
Urinalysis	X	Urine to be checked for protein, glucose, blood, leukocyte esterase, specific gravity, and pH. Microscopic examination of sediment will be done if blood, protein, or leukocyte esterase is significantly positive on dipsticks.
Serology Tests	X	Repeat the following if > 6 months since last treatment: hepatitis B surface antigen, hepatitis C antibody (if hepatitis C antibody is positive reflex to hepatitis C RNA), or hepatitis C RNA. Note: Testing for HIV-1 and HIV-2 must be performed at sites where mandated by local requirements.
Thyroid Function Tests	X	TSH with free T3 and free T4.
Pregnancy Test	X	WOCBP only, at screening and within 24 hours prior to dosing. The serum pregnancy test may be completed on the first day of treatment provided the results are available before the start of study drug. If performed within 24 hours of dosing on Cycle 1 Day 1, then Cycle 1 Day 1 pregnancy test is not required.

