Follicle Stimulating Hormone	X	If needed to document postmenopausal status as defined in Section 3.3.3 .
Efficacy Assessments		
Diagnostic Imaging	X	CT with contrast is the preferred modality (MRI if CT is not feasible). Assessment should include the chest/abdomen/pelvis at a minimum; and should include other anatomic regions as indicated by individual subject disease histories.
Brain Imaging	X	Brain imaging (CT/MRI) only required for subjects with history or symptoms of brain metastases and have not had brain imaging within 30 days of anticipated first study drug administration.
Bone Scan Imaging	X	As clinical indicated (eg, subjects with history or symptoms of bone metastases), but bone scans will not be considered a modality for assessment for measurable disease.
Clinical Drug Supplies		
Subject Registration via IVRS	X	Ensure subject continues to meet eligibility for protocol treatment.

^a All procedures for re-treatment eligibility will be performed within 28 days of re-treatment Day 1 dosing unless noted otherwise.

Abbreviations: ALT = alanine aminotransferase; AST = aspartate aminotransferase; BUN = blood urea nitrogen; CBC = complete blood count; CRP = C-reactive protein; CT = computed tomography; ECG = electrocardiogram; ECOG = Eastern Cooperative Oncology Group; GGT = gamma-glutamyl transferase; HIV = human immunodeficiency virus; LDH = lactate dehydrogenase; LFT = liver function test; MRI = magnetic resonance imaging; PE = physical examination; RNA = ribonucleic acid; TSH = thyroid-stimulating hormone; WOCBP = women of childbearing potential.

Table 5.1-9: Re-treatment Procedural Outline (CA017003 Dose Escalation Part 1 and Dose Expansion Part 2)

Procedure	Cycle 1			Cycles 2+			End of Treatment ^{a,b,c}	Notes
	Day 1	Day 15 (± 2 days)	Day 22-28 (± 2 days)	Day 1	Day 15 (± 2 days)	Day 22 (± 7 days) ^d		
Safety Assessments								
IVRS	X	Q2W Nivo Dosing Only		X	Q2W Nivo Dosing Only			Once subject eligibility has been confirmed, IVRS assignment can be performed within 3 days prior to first study drug administration. (Discuss with Sponsor if institutional policies and procedures require additional lead-time.)
Complete Physical Examination	X			X				Predose
Symptom-directed PE		X			Q2W Nivo Dosing Only		X ^a	Predose

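### Part 1/2 re-treatment (Table 5.1-9) schedules no on-treatment ECG, so after Day 0 the QTcF >500 msec rule has no scheduled measurement behind it

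*Combined protocol and SAP*

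**What the plan says.** Section 3.1.4 allows re-treatment case by case. Subjects who completed about 48 weeks, or who stopped because of a complete response, "may be eligible for re-treatment upon subsequent confirmed disease progression within 12 months of the last dose of study drug". They "will be treated for a maximum duration of 2 years from first dose of nivolumab", normally at the dose first assigned. The only reduction in assessments that this section announces is "Samples for PK will be collected less frequently".

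Section 5.1 gives re-treatment its own tables. Table 5.1-8 covers Day 0 and includes an ECG: "12-lead ECG should be recorded after the subject has been supine for at least 5 minutes if not done within the last 30 days". Table 5.1-9, "Re-treatment Procedural Outline (CA017003 Dose Escalation Part 1 and Dose Expansion Part 2", covers the treatment cycles for Parts 1 and 2. Its safety rows are IVRS, two kinds of physical examination and vital signs, followed directly by laboratory tests. There is no ECG row.

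The schedule for the first course in the same subjects, Table 5.1-3, states "ECGs must be collected predose on Day 1 of each cycle". The Part 3 re-treatment tables (5.1-10 to 5.1-12) state "ECGs must be collected at predose on Day 1 of each cycle".

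Table 4.5.3-1 and Section 4.5.4 act on the criterion "QTcF > 500 msec confirmed by at least 1 repeat ECG and at least 60 msec above baseline". The combination column of Table 4.5.3-1 covers Parts 1, 2 and 3, and neither place exempts re-treatment.

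**The concern.** A rule that modifies or delays dosing on a measured value works reliably only if the value is measured on a schedule. A site that follows Table 5.1-9 to the letter gives BMS-986205 every day in every cycle and records no planned ECG after Day 0. Asymptomatic QTcF prolongation would then be found only if someone ordered an ECG for another reason. The protocol treats the question as open enough to run a QTc substudy, and it reports in vitro hERG inhibition with an IC50 of about 1.1 to 1.2 µM (Sections 1.4.2 and 1.5.1). No efficacy endpoint or analysis is affected; what is at stake is the consistency of safety monitoring.

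**Working it through.** The plan gives no figure to reproduce, so the check is a comparison of tables followed by simple arithmetic on exposure.

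**1. Tables that schedule combination treatment.**

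| Table | Setting | On-treatment 12-lead ECG |
|---|---|---|
| 5.1-3 | Parts 1/2, first course | Day 1 of each cycle |
| 5.1-4 | Part 3 melanoma and mixed | Day 1 of each cycle |
| 5.1-5 | Part 3 NSCLC | Day 1 of each cycle |
| 5.1-6 | Part 3 bladder | Day 1 of each cycle |
| **5.1-9** | **Parts 1/2, re-treatment** | **none** |
| 5.1-10 | Part 3 re-treatment, melanoma | Day 1 of each cycle |
| 5.1-11 | Part 3 re-treatment, NSCLC | Day 1 of each cycle |
| 5.1-12 | Part 3 re-treatment, bladder | Day 1 of each cycle |
| 5.1-15 | QTc substudy, combination | Day 1 of each cycle |

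Eight of nine have the row. Cycles last 4, 6 or 8 weeks depending on the regimen, so one per cycle is not one common calendar interval. A row lost in reading the PDF is unlikely: the abbreviation list under Table 5.1-9 does not define ECG, while the lists under the other eight do.

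**2. Any other scheduled source.** Table 5.1-8 gives the single Day 0 ECG. Table 5.1-13 (re-treatment follow-up) has none. Sections 1.1.9.1 and 1.5.1 promise ECG monitoring in general terms and set no re-treatment time point. Scheduled ECGs in Part 1/2 re-treatment after Day 0: 0.

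**3. Is the ECG the only item dropped?** No. Compared with Table 5.1-3, Table 5.1-9 also drops oxygen saturation, post-infusion vital signs (predose only), the Cycle 1 Day 8 visit and end-of-treatment methemoglobin. The Part 3 re-treatment tables are thinned too: Cycle 1 visit days fall from 7 to 4 in melanoma and from 6 to 4 in NSCLC and bladder. They nevertheless keep the ECG.

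**4. How long the gap can last.** Four-week cycles available = (cap − first course − off-treatment gap) / 4, in weeks. The cap is 2 years, taken as 104 weeks, or as 96 weeks because Section 3.1.2 equates 96 weeks with 2 years. The gap runs from 0 to 52 weeks.

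| First course | Gap | 104-week cap | 96-week cap |
|---|---|---|---|
| 48 | 0 | 56/4 = 14 | 48/4 = 12 |
| 48 | 12 | 44/4 = 11 | 36/4 = 9 |
| 48 | 26 (illustration) | 30/4 = 7.5 | 22/4 = 5.5 |
| 48 | 52 | 4/4 = 1 | −4, so 0 |
| 24, stopped for CR (assumed) | 12 | 68/4 = 17 | 60/4 = 15 |

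The 12-week gap is the first scheduled post-treatment scan in Section 5.4. If that scan is instead the Day 100 visit (14.3 weeks), the 48-week row gives (104 − 62.3)/4 = 10.4 or (96 − 62.3)/4 = 8.4. A subject who used the additional 48 weeks has no time left if progression is found at the first scan, since 96 + 12 = 108 exceeds 104.

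**The case against.** The strongest reply is that Table 5.1-9 is a deliberately lighter schedule. It drops several other safety items that Section 3.1.4 does not announce, so that section is no full list of what was reduced. The Part 3 tables follow a heavier template for a triplet with 13 treated subjects and repeated DLTs at the time of writing, against 397 subjects on the doublet. This stands to one extent: a reader might infer that the missing row is a proven drafting error, and the documents do not support that. They are equally silent on any reason for dropping it, and neither explanation gives the QTcF rule a scheduled input.

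A second reply is that the risk is small. Re-treated subjects must still meet eligibility, which excludes QTcF of 480 msec or more. They had an ECG every cycle on the first course and generally return to the same dose. Section 1.1.9.1 regards nivolumab as having no QTc effect. In vitro test concentrations were at least 580 times free Cmax at 100 mg, and dogs showed no ECG change at 8 times Cmax. Electrolytes are checked each cycle. All of this stands. A reader might infer from the gap that cardiac harm is expected; the protocol's own assessment is low cardiovascular risk, and nothing in the documents contradicts it.

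A third reply is that Section 3.1.4 sends re-treated subjects to the same Section 5 schedule, which could mean the original one. Section 5 contains a dedicated Part 1/2 re-treatment table, however, and that is the one a site would open. If Table 5.1-3 is meant, the two tables conflict on ECGs and the sponsor still has to say which governs.

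**Conclusion.** The point holds as a gap in scheduled monitoring. Table 5.1-9 is the only one of nine combination-treatment tables without an on-treatment ECG. After a Day 0 ECG that may itself be waived, the QTcF >500 msec rule rests on unscheduled ECGs alone.

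The possible duration after a 48-week first course is 1 to 14 cycles under a 104-week cap and 0 to 12 under a 96-week cap. The upper ends assume a zero-week gap; 8.4 to 11 cycles applies if progression is found at the first scheduled scan and dosing resumes at once. It would be wrong to read 14 as a ceiling for every subject, because those who stopped early for a complete response are also eligible and could have more.

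The affected group is limited to case-by-case approvals and excludes subjects who stopped for drug-related toxicity. Its size is not stated and could be zero. The change should be made because it is cheap and restores the measurement that a stated rule needs.

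**What to change.** Add the Table 5.1-3 row to Table 5.1-9 at the next amendment: 12-lead ECG, predose, Day 1 of each cycle. All nine tables would then agree. If the omission was intended, state that in Section 3.1.4 and say how the QTcF rule is to operate during re-treatment.

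The cost is a table correction and one routine ECG per four-week re-treatment cycle, at Day 1 visits that already take place. That is at most 14 per subject after a 48-week first course under a 104-week cap (12 under a 96-week cap), and possibly more for a subject who stopped earlier in complete response.
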